### 5.2 Participant Disposition

The summary of study disposition will be done for all screened participants overall and by treatment group as randomized. Number and percentages are based on the numbers of participants in their randomized allocations. The following will be provided:

- Number of participants screened (overall)
- Number of participants randomized (this number will be used as denominator to compute the following percentages)
- Number of participants treated as randomized
- Number of participants not treated as randomized

For mITT population during CP:

- Number of participants completed CP
- Number of participants discontinued during CP
- Reasons for discontinuation during CP

For VIT and VOT population during PCP:

- Number of participants who continued into PCP
- Number of participants who completed PCP
- Number of participants who discontinued during PCP
- Reasons for discontinuation during PCP

For mITT population during the study:

- Number of participants who completed the study
- Number of participants who discontinued from the study
- Reasons for discontinuation from the study

Treatment group participants are considered to have completed the study if they complete the Month 12 visit in the Post-Control Period. Control group participants who elect not to receive optional treatment are considered to have completed the study if they complete the Month 6 visit in the Control Period. Meanwhile, control group participants who elect to receive optional treatment are considered to have completed the study if they complete the Month 6 visit in the Post-Control Period.

In addition, a listing will be provided for participant disposition.

# 6.0 Study Device Exposure and Administration

Treatment exposure-related variables will be summarized for the VIT and VOT populations. For the VOT population, data after participants received the initial treatment at Month 6 are included. Study treatment exposure will be measured by volume injected at each treatment (Table 3) and summarized by treatment group, treatment (initial, touch-up, initial and touch-up combined), and treatment area.

#### Table 3.Exposure to Study Treatment

Endpoint	Description	Timing	Methodology	
Number (%) of participants received treatment	Summary by treatment group, treatment (initial, touch-up)	Initial, Touch-up	Frequency counts and percentages	
Injection volume 
 
Total
 
Left temple
 
Right temple
 
	Summary by treatment group, treatment (initial, touch-up, initial and touch-up combined), and treatment area	Initial, Touch-up, Initial and Touch-up combined	Continuous descriptive statistics	

The number of participants who received treatment anesthesia will be summarized for the VIT and VOT populations. Variables related to administration of treatment listed in Table 4 will be summarized for the VIT and VOT populations by treatment group, treatment area (right and left temple area), and treatment (initial, touch-up).

#### Table 4. **Administration of Study Treatment**

Endpoint	Description	Timing	Methodology	

 
Pre-treatment anesthesia type
 
Ice
 
Topical
 
Local injection
 
	Summary by treatment group and treatment (initial, touch-up)	Initial, Touch-up	Frequency counts and percentages	

 
Pre-treatment anesthesia duration (minutes) for each pre-treatment anesthesia type 
 
Anesthesia duration is computed as the earlier injection time of the two temples minus start of anesthesia administration time. Summarize by treatment group, treatment, and anesthesia type.
 
 
 
	Summary by treatment group and treatment (initial, touch-up)	Initial, Touch-up	Continuous descriptive statistics	

 
Treatment administration
 
Needle useda (27 Gauge 1/2 inch, 25 Gauge 1 inch, other)
 
Number of injections per temple
 
Planes of injectiona (supraperiosteal, other)
 
Injection techniquea (bolus, other)
 
Total number of syringes usedb
 
Device/needle problem or malfunctionb
 
	Summary by treatment group, treatment (initial, touch-up) and treatment area (left temple, right temple)	Initial, Touch-up	Frequency counts and percentages, continuous descriptive statistics	

Treatment characteristics

Injection ease

Product moldability

	Summary by treatment group and treatment (initial, touch-up)	Initial, Touch-up	Frequency counts and percentages, continuous descriptive statistics	

A participant may be counted in multiple planes of injection, injection techniques, and types of needles used. a.

Total number of syringes used and device/needle problem or malfunction will not summarized by treatment area. b.

A listing will be provided for extent of exposure and treatment administration.

# 7.0 Demographics, Baseline Characteristics, Medical History, and Prior/Concomitant Medications

#### 7.1 Demographics and Baseline Characteristics

Demographic parameters (age; age group; sex; race) will be summarized descriptively in total and by treatment group for the mITT populations. Age (years) is calculated relative to informed consent date.

Baseline characteristics shown below will be summarized descriptively in total and by treatment group for the mITT populations:

- Weight (kg), height (cm), and BMI (kg/m^2)
- Allergan Temple Hollowing Scale
- FACE-Q Satisfaction with Facial Appearance questionnaire, for the Raschtransformed score
- FACE-Q Satisfaction with Temples questionnaire, for the Rasch-transformed score
- Jaw Functional Limitation Scale
- Self-perception of age

Demographic and baseline characteristics will be provided in a listing.

#### 7.2 Medical History

Abnormalities in participants' medical, surgical, cosmetic, and dental history, encompassing abnormalities, surgeries, and procedures reported as occurring before the Screening visit, will be coded using the Medical Dictionary for Regulatory Activities (MedDRA). The actual version of the MedDRA coding dictionary will be noted in the statistical outputs and clinical study report.

Listing will be provided for the safety population.

#### 7.3 Prior and Concomitant Medications

The medication data will be coded using the World Health Organization (WHO) Drug Dictionary. The actual version of the WHO Drug Dictionary will be noted in the statistical outputs and clinical study report. Prior medication is defined as any medication taken prior to the latter of randomization date or first treatment date in the control period. Concomitant medication is defined as any medication taken on or after the latter of randomization date or first treatment date in the control period.

Listing will be provided for the safety population. The Anatomical Therapeutic Chemical (ATC) class, and preferred drug name will be presented (i.e., 4th level, or most specific level available if 4th level is unavailable).

# 8.0 Effectiveness Analyses

#### 8.1 General Considerations

- For CP, effectiveness analyses and baseline characteristics will be performed on the mITT population. Subjects will be included in the analysis according to the treatment groups that they are randomized to.
- For TP, effectiveness analysis will be performed on the VIT and VOT populations. Subjects will be included in the analysis according to the study treatment that they actually received.
- The baseline for effectiveness parameters will be the last non-missing assessment prior to or on Day 1, i.e., the latter of randomization or initial injection in Control Period.
- Day 1 is defined as the day on which the study intervention (VOLUMA or notreatment control) is first received.
- Study day refers to Day 1 regardless of study period (e.g., CP, TP).
- The change from baseline values will be computed as the postbaseline value minus the baseline values.
- Continuous variables will be summarized by number of participants with observed values (n), mean, standard deviation (SD), median, 1st and 3rd quartiles (Q1, Q3), minimum (min), and maximum (max). Categorical

variables will be summarized by the number of participants with observed values or events (n) and the percentage of participants with observed values or events.

- All statistical hypothesis tests will be performed at the 2-sided, 5% significance level, unless stated otherwise.
- All CIs will be 2sided 95% CIs, unless stated otherwise.
- All statistical analyses will be performed using SAS Version 9.4 or subsequent.

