#### Table 1.Analysis Sets

Population	Definition	Study Intervention
Modified Intent -to Treat (mITT)	All randomized participants who have non-missing baseline ATHS assessment for both temples.	As randomized
Observed Primary Endpoint (OPE)	All mITT population participants who have non-missing Month 6 ATHS assessments for both temples.	As randomized
Per-Protocol (PP) All mITT population participants who have non-missing month 6 ATHS assessments for both temples and do not have any significant protocol deviations affecting the primary effectiveness endpoint. (i.e., a significant deviation that occurs after the primary endpoint does not lead to exclusion from the PP population.)		As randomized
Safety	All participants who are randomized and received study intervention (VOLUMA or no-treatment control).	As treated
VOLUMA Initially Treated (VIT)	All safety population participants who were randomized and received VOLUMA treatment at the beginning of the Control Period.	As treated
VOLUMA Optionally Treated (VOT)	All safety population participants who were randomized to control group and received VOLUMA optional treatment after the Control Period.	As treated

The number of participants in each of the 6 study populations (mITT, OPE, PP, Safety, VIT and VOT) will be summarized by treatment group, if applicable.

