#### 8.5 Additional Effectiveness Analyses

The other effectiveness analyses will be performed for all variables listed in Table 7. Analyses on the primary and secondary variables at other visits will be performed. All analyses are based on observed data and missing data will not be imputed. All analyses are performed by treatment group and by visit. Additionally, no hypothesis will be tested and, thus, no multiplicity adjustment will be performed.

For CP, the mITT population will be used, including Month 1, 3 and 6 visits.

For TP of the VOLUMA group, the VIT population will be used, including Month 1, 3, 6, 9 and 12 visits.

For TP of the control group, the VOT population will be used, including Month 1, 3 and 6 visits.

In the responder analysis on FACE-Q Satisfaction with Facial Appearance and Satisfaction with Temples questionnaires, a responder is defined as any participant whose postbaseline Rasch-transformed score is greater than their baseline Rasch-transformed score.

For the descriptive summary of ATHS overall score, the temple with worse baseline score will be used to represent the participant; if both temples have he same baseline score, the left side temple will be used to represent the participant.

For participant's self-perception of age in treatment group, change from baseline (e.g., -10 ="I look 10 years younger," 0 ="I look my age," and +6 ="I look 6 years older") will be calculated and summarized descriptively. The paired t-test nominal p-value will be calculated at Month 6 as descriptive guidance to consider if the change from baseline is different from zero for the primary timepoint of Month 6.

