#### Table 7. **Other Effectiveness Analyses**

Endpoint	Description	Analysis Period	Methodology
ATHS responder status as assessed by EI	Number (%) of responders	CP, TP	Binomial descriptive statistics
Raw value and change from baseline in ATHS score as assessed by EI (based on the worse temple, or the left temple if both temples have the same baseline score)	Summary	CP, TP	Continuous descriptive statistics
GAIS responder status as assessed by EI	Number (%) of responders	CP, TP	Binomial descriptive statistics
Responses on GAIS as assessed by EI	Number (%) by response category	CP, TP	Frequency counts and percentages
GAIS responder status as assessed by participant	Number (%) of responders	CP, TP	Binomial descriptive statistics
Responses on GAIS as assessed by participant	Number (%) by response category	CP, TP	Frequency counts and percentages
Raw value and change from baseline in FACE-Q Satisfaction with Facial Appearance Rasch-transformed score as assessed by participant	Summary	CP, TP	Continuous descriptive statistics
Responder status in FACE-Q Satisfaction with Facial Appearance Rasch-transformed score as assessed by participant	Number (%) of responders (improved)	CP, TP	Binomial descriptive statistics
Responses on item A, F, J of FACE-Q Satisfaction with Facial Appearance	Number (%) by response category (including somewhat satisfied or very satisfied)	CP, TP	Binomial descriptive statistics
Responses on each item of FACE-Q Satisfaction with Facial Appearance	Number (%) by response category	CP, TP	Frequency counts and percentages

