# 9.0 Safety Analyses

#### 9.1 General Considerations

- For CP, safety summaries will be performed on the safety population. Subjects will be included in the analysis according to the study treatment that they actually received.
- For TP, safety summaries will be performed on the VIT and VOT populations. Subjects will be included in the analysis according to the study treatment that they actually received.
- The baseline for safety parameters will be the last non-missing assessment prior to or on Day 1, i.e., the latter of randomization or initial injection in Control Period. Day 1 is defined as the day on which the study intervention (VOLUMA or no-treatment control) is first received.
- Study day refers to Day 1 regardless of study period (e.g., CP, TP).
- The change from baseline values will be computed as the postbaseline value minus the baseline values.
- Adverse events (AEs) will be coded using the Medical dictionary for Regulatory Activities (MedDRA). The actual version of the MedDRA coding dictionary will be noted in the statistical tables and clinical study report.

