## 9.10 Other Safety Analyses

Other safety endpoints include global score of jaw functional and concomitant medication and concurrent procedures.

The other safety endpoints will be summarized by treatment groups, for VIT and VOT where applicable.

For Jaw Functional Limitation Scale, the 8-item form (JFLS-8) is used in the study. Raw and change from baseline values of global score (calculated as mean of the available items when no more than 2 items missing) will be summarized using descriptive statistics.

Concomitant medications (Section 7.3) and concurrent procedures (coded using MedDRA) will be listed.

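### For controls who take the optional injection, planned change and responder summaries start at randomization, about six months before that injection; supplementary rows based on the pre-injection score would show change since injection

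*SAP*

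**What the plan says.** SAP 8.1 defines the effectiveness baseline: "The baseline for effectiveness parameters will be the last non-missing assessment prior to or on Day 1". It explains Day 1 as "i.e., the latter of randomization or initial injection in Control Period" and adds that study day counts from that same Day 1 in both the control and the treatment period. SAP 9.1 repeats the rule for safety: "The baseline for safety parameters will be the last non-missing assessment prior to or on Day 1". Protocol 9.4.1 also places the effectiveness baseline before randomization and has no separate rule for optional treatment.

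SAP Table 1 defines VOT as "All safety population participants who were randomized to control group and received VOLUMA optional treatment after the Control Period". SAP 5.1 and Table 2 start these participants' treatment period on the day of the optional injection. No section or appendix gives them a new baseline.

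The summaries concerned are:

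- **ATHS.** SAP Table 7 lists "Raw value and change from baseline in ATHS score as assessed by EI" and ATHS responder status for both periods. SAP 8.5 sets the populations: "For TP of the control group, the VOT population will be used, including Month 1, 3 and 6 visits" and "For CP, the mITT population will be used, including Month 1, 3 and 6 visits".
- **Jaw scale.** SAP 9.10 plans "Raw and change from baseline values of global score" for VIT and VOT where applicable, and names no time points.
- **FACE-Q and 3D volume.** SAP Table 7 lists change from baseline in both periods.

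Protocol Table 1-3 puts the optional initial injection on the same day as the control Month 6 visit. ATHS, FACE-Q and 3D imaging are scheduled at that visit. The jaw scale is scheduled at the optional initial treatment itself, with a footnote requiring completion before the injection. (The footnote letter is garbled in the text available; I read it as f.)

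**The concern.** A reader will take the VOT tables as showing what happened after the optional injection. As specified, they show what happened since randomization, with about six untreated months included. VIT has no such lead-in, so two sets of post-injection tables would measure different things.

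This matters most where the outcome is classified participant by participant, as with ATHS responder status, and where it bears on an expected local reaction, as with the jaw scale. Protocol 2.2 cites an open-label study in which 40% (12/30) reported jaw pain on chewing after the initial treatment. A jaw-score change that arose during the untreated months would be summarized as change after injection, or could mask one.

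**Working it through.** **1. Which day is Day 1 for a VOT participant.** A control has no injection in the control period, so the later of randomization and control-period injection is randomization. Nothing resets it for the treatment period.

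**2. Untreated days between baseline and injection.** SAP Table 2 gives a Month 6 target of 180 days. Protocol Table 1-3 gives a window of ±2 weeks (14 days) and same-day injection.

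- Shortest: 180 − 14 = 166 days. Longest: 180 + 14 = 194 days.
- If six calendar months (181 to 184 days) are used instead: 181 − 14 = 167 to 184 + 14 = 198 days.
- If only a screening score exists (screening up to 30 days): up to 194 + 30 = 224 days.
- VIT with a Day 1 score: 0 days, since randomization and first injection fall on the same day. The screening allowance applies to VIT as well, so it does not create the difference between groups.

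**3. Share of the baseline-to-assessment time that precedes any injection.** Share = untreated days ÷ (untreated days + days since the initial injection), taking Month 1 as 30 to 37 days.

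| VOT assessment | Low | High |
|---|---|---|
| Day 14 jaw score after initial injection | 166/(166+14) = 92.2% | 194/(194+14) = 93.3% |
| Month 1, no touch-up | 166/(166+37) = 81.8% | 194/(194+30) = 86.6% |
| Month 6, no touch-up | 166/(166+194) = 46.1% | 194/(194+166) = 53.9% |
| Month 6, with touch-up | 166/(166+37+194) = 41.8% | 194/(194+30+166) = 49.7% |

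These are shares of time. If untreated change is zero, the distortion is zero at any share.

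**4. Effect on a mean.** For each participant,

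(post − Day 1) = (pre-injection − Day 1) + (post − pre-injection).

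An average untreated shift of d among those who opted in therefore moves the VOT mean change by exactly d. The documents give no value for d.

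**5. Effect on responder status.** A responder improves by at least 1 grade on both temples. With both temples alike:

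| Day 1 | Pre-injection | Post | From Day 1 | From pre-injection |
|---|---|---|---|---|
| 3 | 2 | 2 | responder | nonresponder |
| 3 | 3 | 2 | responder | responder |
| 2 | 3 | 2 | nonresponder | responder |

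The classification can differ in either direction. Each participant who differs moves the VOT rate by 1/45 = 2.2 points if 45 opt in (the planned evaluable controls). With 50% uptake, an assumption, it is 1/23 = 4.3 points. How many differ is unknown.

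**6. What other planned tables recover.**

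- *Jaw scale mean.* If the raw pre-injection mean is tabulated under SAP 9.10, subtraction gives approximate mean change since injection, apart from missing data.
- *ATHS mean.* Control Month 6 ATHS is summarized for all mITT controls, not for those who opted in. Subtraction approximates VOT change well only if nearly all opt in.
- *ATHS responder status.* This is a per-participant rule on two temples and cannot be rebuilt from group rates.

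**The case against.** The best defence is that a single baseline is a coherent choice. Protocol 9.4.1 uses it, the GAIS is rated against baseline photographs, and eligibility rests on the enrolment ATHS. No qualifying grade is required again at Month 6, so a pre-injection reference could include temples at Grade 0 or 1, and a temple at Grade 0 cannot gain a grade. This stands. It is a reason to keep the Day 1 rows, not a reason to leave out the others.

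Second, nothing in the documents shows that temples change much untreated. Planned weight change above 10% is an exclusion, and other facial procedures are prohibited. A one-grade shift may be rating variability, which affects VIT too. This also stands: the examples in step 5 show that the rule can reclassify participants, not how often it will.

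Two stronger inferences are tempting but unsupported. One is to read the 92–93% or 46–54% shares as the fraction of the VOT result that is spurious; they count days only. The other is to take the 35% control responder rate in Protocol 9.2 as the size of the problem. The protocol presents it as an upper limit of expectation, and part of it may be rating variability, which would appear in VIT under a Day 1 baseline as well.

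Third, jaw safety does not rest on the JFLS-8 alone. Adverse events in VOT are summarized, and treatment-related events by time to onset from the most recent treatment. That is correct and limits the consequence.

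Finally, the pre-injection order of the control Month 6 ATHS is inferred. Unlike the jaw scale, that entry has no footnote requiring it before the injection, and Protocol 1.3 leaves sequence optional unless specified. The inference is sound, because the rating is the control arm's untreated primary endpoint, but it should be written down.

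**Conclusion.** The point holds as a minor one. The SAP measures VOT ATHS change, ATHS responder status, JFLS-8 change, FACE-Q change and 3D volume change from a score about 166 to 194 days before the optional injection, with no counterpart in VIT. These figures assume the SAP's 180-day target, an in-window Month 6 visit and a Day 1 score. Untreated change is mixed with change since injection, by an amount the documents do not allow to be estimated.

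A reader might infer that change since injection cannot be recovered at all. That goes too far: mean change may be approximated from other tables as in step 6, and only per-participant responder status since injection is out of reach. A reader might also infer that the effectiveness conclusion is at risk. It is not. The VOT effectiveness summaries test no hypothesis, and the primary, gated and other control-period results use the control period only.

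**What to change.** In SAP 8.5 and 9.10, keep the Day 1-based VOT rows and add supplementary VOT rows that take the last non-missing score before the optional initial injection as reference:

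- **Control Month 6 visit:** ATHS change and ATHS responder status, with the pre-injection grade distribution; FACE-Q change; 3D volume change.
- **Optional initial treatment visit:** JFLS-8 change.

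State that the control Month 6 ATHS is to be rated before the injection. Leave participants without a pre-injection score out of the added rows and report how many that is. For ATHS change, use the temple already selected on Day 1, so that the two rows differ only in the reference score. Self-perception of age has no pre-injection value in Protocol Table 1-3, and the GAIS is tied to baseline photographs, so neither needs a new row.

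The cost is a few descriptive rows from data already scheduled, with no new visit, form or test. The downside is that each added row relies on a single pre-injection assessment with its own variability.
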